Exparel® is an FDA-approved non-opioid local anesthetic that is approved for single-dose infiltration to produce post-surgical local anesthesia for patients six years and older.¹² Exparel® is composed of a liposomal bupivacaine formulation that allows retention of local anesthetic at the site of injection to allow for durations as long as 72 hours.¹² Exparel® may take 3-4 hours to exert maximum analgesic effect and thus it is approved for either sequential administration or admixing with other local anesthetics such as 0.25% Marcaine. To date, no studies have evaluated the use of this local anesthetic in children undergoing urologic procedures. Exparel® may serve as a valuable tool in the pediatric urologists' pain control armamentarium to safely and effectively provide long-lasting non-opioid pain control and may allow for the reduction of elimination of opioid medications in this population.

In the present study, we will compare Exparel® plus 0.25% Bupivacaine to standard 0.25% Bupivacaine as a perioperative local analgesic. We will also simultaneously assess whether inclusion of opioid disposal instructions improved proper disposal of leftover opiate medication following the immediate postsurgical period.

4. Study Procedures

- a. Study design, including the sequence and timing of study procedures (distinguish research procedures from those that are part of routine care).

Date: 12/1/2021

Principal Investigator: [name] [name]

Application Number: IRB00284462

ClinicalTrial.gov Identifier: NCT04826484

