This study will be a single-blinded prospective randomized trial in pediatric patients undergoing minor urologic surgery. Pediatric patients will be randomized in a 1:1 fashion to receive dorsal penile nerve block (circumcision, hypospadias repair, penile cyst excision, meatoplasty, chordeolysis) or spermatic cord block with local wound infiltration (orchiopexy, orchiectomy, inguinal hernia, hydrocelectomy, varicocelectomy) with Exparel® plus 0.25% Bupivacaine versus standard 0.25% Bupivacaine alone. Patient families will also be cross randomized in a 1:1 fashion to receive standard post-operative pain instructions, with or without opioid disposal instructions. Families that consent to participation in the trial will be informed of randomization to Exparel® plus 0.25% Bupivacaine versus standard 0.25% Bupivacaine but will be blinded to arm assignment. Families will also be informed that they will be receiving postoperative pain instructions, however they will not be informed of whether or not they receive opioid disposal instructions.

No other standard pre-, peri- or post-operative pediatric urologic surgery procedures will be affected. Routine care includes an initial clinic consultation, physical examination, and informed consent prior to proceeding with surgery. Informed consent for participation in the study may also be obtained in the preoperative area during the day of surgery. Eligibility will be confirmed at the time of consent. Patient will be randomized after consent is obtained and appropriate postoperative pain instructions with or without opioid disposal instructions will be given at that time to minimize drop out.

Anesthesia team will be notified when local wound infiltration or penile nerve block is being performed as is standard operating procedure, however we will not dictate what other intra or peri-operative analgesia is given. All blocks will be performed by the surgical team using landmark techniques.

Patients will be given the option of returning to the Johns Hopkins clinic or local follow-up (with a provider) for wound check approximately 7-14 days after surgery.

[figure not shown]

Figure 1. Diagram of plan for stratified randomization of patients to arms and outcomes assessed.

Date: 12/1/2021

Principal Investigator: [name] [name]

Application Number: IRB00284462

ClinicalTrial.gov Identifier: NCT04826484

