- b. If your study involves data/biospecimens from participants enrolled under other research studies with a written consent or under a waiver of consent, please list the IRB application numbers for those studies. Please note: Certificate of Confidentiality (CoC) protections applied to the data in source studies funded by NIH or CDC will extend to this new study if the funding was active in 2016. If this situation applies, Section 36, question 6 in the application will need to be answered “Yes” and “Hopkins Faculty” should be selected in question 7. No other documents are required.

N/A

- c. Study duration and number of study visits required of research participants.

The study protocol will be implemented during routine visits and minor pediatric urologic surgery. This includes patients undergoing orchiopexy, orchiectomy, circumcision (primary and revision), distal hypospadias repair, meatotomy/meatoplasty, chordee repair, penile cyst excision, urethrocutaneous fistula repair, inguinal hernia repair, hydrocelectomy, and varicocelectomy. Patient will receive normal postoperative follow up for a wound check and will receive phone correspondence at 48 hours and 10-14 days postoperatively to collect data regarding opioid prescribing, opioid use, pain, and disposal.

- d. Blinding, including justification for blinding or not blinding the trial, if applicable.

Pediatric randomized in a 1:1 fashion to receive dorsal penile nerve block or spermatic cord block with local wound infiltration with Exparel® plus 0.25% Bupivacaine versus standard 0.25% Bupivacaine. Families will consent to enrollment in the trial to receive either Exparel® plus 0.25% Bupivacaine or standard Bupivacaine but will remain blinded to which local anesthetic is given intraoperative to ensure there is no bias between arms with respect to opioid administration or postoperative pain expectations by the family. Consent for the trial will be performed by the study coordinator and surgeons will not be aware of treatment allocation until patient is in the operating room and block is ready to be administered.

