4. Unwilling or unable to participate in 48 hours and 10-14 day follow-up phone calls

6. Drugs/ Substances/ Devices

- a. The rationale for choosing the drug and dose or for choosing the device to be used.

Exparel® is composed of a liposomal bupivacaine formulation that allows retention of local anesthetic at the site of injection to allow for durations as long as 72 hours.¹² To date, no other long lasting non-opioid pain control exists for pediatric patients undergoing surgery.

Date: 12/1/2021

Principal Investigator: [name] [name]

Application Number: IRB00284462

ClinicalTrial.gov Identifier: NCT04826484

Per the Exparel® dosing and administration guide, the maximum recommended dose for Exparel® is 4 mg/kg. Bupivacaine may be given concurrently with Exparel as long as the ratio of the milligram dose of bupivacaine HCl to Exparel does not exceed 1:2 (50% of the mg dose of Exparel).¹² Each Exparel® contains 133 mg of liposomal bupivacaine in 10 ml saline, or 13.3 mg/ml. 0.25% bupivacaine contains 2.5 mg/ml of bupivacaine. Patients randomized to the intervention arm received sequential weight-based administration of 0.5 mg/kg (maximum recommended dose 2.5 mg/kg) of 0.25% bupivacaine hydrochloride without epinephrine followed by 2.5 mg/kg (maximum recommended dose 4 mg/kg) of 1.33% liposomal bupivacaine such that the ratio of the milligram dose of bupivacaine hydrochloride to liposomal bupivacaine did not exceed 1:2 (50% of the mg dose of liposomal bupivacaine) as described in the medication dosing insert.

- b. Justification and safety information if FDA approved drugs will be administered for non-FDA approved indications or if doses or routes of administration or participant populations are changed.

Exparel® is an FDA-approved non-opioid local anesthetic that is approved for single-dose infiltration to produce post-surgical local anesthesia for pediatric patients six years and older.¹²

- c. Justification and safety information if non-FDA approved drugs without an IND will be administered.

N/A

7. Study Statistics

- a. Primary outcome variable.

The primary efficacy endpoints will be the percentage of pediatric patients who are opiate-free at 48 hours and at 10-14 days postoperatively, parents' postoperative pain measure (PPPM) scores at 48 hours and 10-14 days postoperatively, amount of opioid used following discharge (as measured by weight based oral morphine equivalents), and the amount of opioid leftover at 10-14 days.

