The primary safety endpoints will be the incidence of pre-defined complications related to local anesthetic systemic toxicity (exceedingly rare in all phase 2 and 3 trials), and the percentage of families properly disposing of leftover opiate medication at 10-14 days postoperatively.

The primary analysis will involve two separate comparisons: 1) Comparison of primary efficacy endpoints between those receiving Exparel® plus 0.25% Bupivacaine versus those receiving standard 0.25% Bupivacaine alone, and 2) Comparison of primary safety endpoints between those receiving Exparel® plus 0.25% Bupivacaine versus those receiving standard 0.25% Bupivacaine alone.

- b. Secondary outcome variables.

Date: 12/1/2021

Principal Investigator: [name] [name]

Application Number: IRB00284462

ClinicalTrial.gov Identifier: NCT04826484

Secondary outcomes will include a cost comparison of Exparel® plus 0.25% Bupivacaine versus standard 0.25% Bupivacaine alone, as well as evaluating efficacy of using Exparel® for a penile nerve block versus incisional infiltration with regard to safety and efficacy.

c. Statistical plan including sample size justification and interim data analysis.

All patients that meet inclusion criteria for the trial and are consented will undergo cross-randomization (Figure 1) to receive either 0.25% Bupivacaine or Exparel® plus 0.25% Bupivacaine, opioid medication instructions with disposal instructions, or opioid medication instructions without disposal instructions.

Currently at Johns Hopkins, we perform over 500 minor pediatric urologic procedures per year, roughly 20% of which involve patients 6 years or older and could be eligible for inclusion.

We assumed that the smallest detectable difference in the primary endpoints may be the percentage of patients who are opiate-free at 48 hours and thus planned to base our power calculation on detecting a difference in this variable. Prior studies from our institution have demonstrated that roughly 28% of pediatric patients undergoing minor urologic procedures and receiving standard Bupivacaine local wound infiltration require zero opioids postoperatively.² This study will be conducted with a superiority design (does penile block or wound infiltration with Exparel® plus 0.25% Bupivacaine offer a superior opiate-free rate at 48 hours than standard Bupivacaine?).

Power of 80% (beta = 0.2) and two-sided alpha of 0.05 for increasing opiate-free rate

28% to 60%: n = 74; 37 in each arm

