28% to 50%: n = 152; 76 in each arm

28% to 40%: n = 486; 243 in each arm

28% of peds uro pts from recent JHH anesthesia study required zero opiates

Consensus among the study investigators suggested that a 50% opioid-free rate at 48 hours (22% absolute difference between arms) would be the minimal clinically relevant difference in the primary outcome measure.

Assuming a 25% rate of lost-to-follow-up or incomplete follow-up data, we will plan to enroll 100 pediatric patients per arm, or 200 patients total. Target enrollment may be subject to change if the lost to follow-up rate is significantly higher or lower than 25%.

Randomization lists will be generated by the study coordinator. The investigators will maintain the randomization list, password protected, on a remote drive maintained by the Department of Urology and will provide the random assignment to the study coordinator as each patient is enrolled.

One interim analysis of the primary efficacy and primary safety endpoint will be planned with potential early stopping for efficacy or futility. The interim analysis will be conducted after half

Date: 12/1/2021

Principal Investigator: [name] [name]

Application Number: IRB00284462

ClinicalTrial.gov Identifier: NCT04826484

of the patients have been enrolled. O'Brien-Fleming boundaries will be used, as implemented in PASS v. 11 (NCSS Software, Inc., Kaysville, UT).

One interim analysis of the primary efficacy endpoint will be conducted after information proportion of 0.66 (n = 102) to assess for early stopping for efficacy or futility. The total sample size needed for 80% power with a 1-sided test was 152 patients (76 per arm), based on 10,000 simulations. Alpha-spending at the interim analysis and final analysis was 0.016 and 0.034 (cumulative alpha spent 0.016, 0.05), respectively. The futility boundaries at the interim analysis and final analysis were p=0.24 and p=0.048, respectively. At the interim analysis the rates of all-cause surgical complications and those attributable to sequela of the local anesthetics or symptoms related to LAST were also evaluated. An unacceptable rate of all-cause surgical complications was >10%. If the lower 95% confidence bounds met or exceeded this rate for all-cause complications or there were any episodes of LAST, the trial would have been halted for further review and consideration of early stopping.

Statistical Analysis

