Local anesthetics are frequently administered by the operating surgeon at the time of minor urologic procedures in pediatric patients. All local anesthetics administered in this study will be done intraoperatively while the patient is being monitored with non-invasive blood pressure and peripheral oxygen saturation measurements. Avoidance of intravascular injection of all local anesthetics will be performed via visual inspection on aspiration prior to injection. Additionally, the surgical team will ensure the administered local anesthetic dose does not exceed the maximal recommended dose (2 mg/kg for Bupivacaine or 4 mg/kg for Exparel). All patients will also be observed in the recovery area postoperatively for at least one hour to ensure none of the aforementioned side effects occur, in accordance with standard practice at Johns Hopkins.

- c. Plan for reporting unanticipated problems or study deviations.
- Unanticipated problems or concerns will be reported by the in-hospital urology team to the research coordinator(s) of the trial as well as the principal investigator. A plan of action will be developed and implemented with open communication with the IRB and appropriate avenues for reporting adverse events. The Hopkins Event Reporting Online (HERO) system can also be utilized as needed.
- d. Legal risks such as the risks that would be associated with breach of confidentiality.
- There are no anticipated legal risks with breach of confidentiality specifically associated with the trial. Those participating in the trial will receive the usual care afforded to all pediatric patients undergoing minor urologic procedures.

- e. Financial risks to the participants.

Both arms of the trial consist of accepted practice standards. Patients and their respective insurance will be responsible for the cost of routine care including surgery and postoperative follow-up which will be unaffected by the study.

9. Benefits

- a. Description of the probable benefits for the participant and for society.

Date: 12/1/2021

Principal Investigator: [name] [name]

Application Number: IRB00284462

ClinicalTrial.gov Identifier: NCT04826484

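### No stated definition, window or post-discharge question supports the LAST endpoint, so late toxicity events and complications may be missed and the safety results and interim safety checks would rest on incomplete counts

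*Combined protocol and SAP*

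**What the plan says.** Section 7a sets the endpoint: "The primary safety endpoints will be the incidence of pre-defined complications related to local anesthetic systemic toxicity". It is to be compared between arms, with rates and adjusted odds ratios under the Statistical Analysis heading of section 7c. Section 7a gives the disposal endpoint a time point of 10-14 days. It gives LAST none, and the available text does not list the pre-defined complications.

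The interim text in section 7c makes LAST a trigger: "or there were any episodes of LAST, the trial would have been halted" for further review. The same sentence sets a second check on all-cause surgical complications, which is met when the lower 95% confidence bound reaches 10%.

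On observation, section 8b says local anesthetics are "done intraoperatively while the patient is being monitored with non-invasive blood pressure and peripheral oxygen saturation measurements", and then: "All patients will also be observed in the recovery area postoperatively for at least one hour".

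On the drug, section 3 says it "may take 3-4 hours to exert maximum analgesic effect", and sections 3 and 6a describe "retention of local anesthetic at the site of injection to allow for durations as long as 72 hours".

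After discharge, section 4c plans calls at 48 hours and 10-14 days "to collect data regarding opioid prescribing, opioid use, pain, and disposal". Section 4a gives families the "option of returning to the Johns Hopkins clinic or local follow-up (with a provider) for wound check" at about 7-14 days. Section 8c routes unanticipated problems through the in-hospital urology team to the coordinators and the principal investigator, and also names the hospital's event reporting system.

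**The concern.** The arms differ by the long-acting component. The guaranteed observation can end before that component reaches the maximum effect the protocol describes, and the patients then go home. If data are collected exactly as listed, a toxicity symptom or complication arising at home reaches the trial only when a family or outside provider happens to report it.

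Three results depend on those counts: the between-arm comparison of a primary safety endpoint, the LAST halt, which turns on a single episode, and the all-cause complication check. A report of no LAST, or of no difference between arms, could not be told apart from a report that nobody asked. Section 3 says the drug has not been studied before in children having urologic procedures, so readers are likely to rely on this trial's safety data.

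**Working it through.** **Timeline from the documents**

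| Time | What the plan describes | Does it ask about toxicity? |
|---|---|---|
| Surgery | Blood pressure and oxygen saturation (8b) | Yes, by monitoring |
| Recovery, minimum 1 h | Observation for the side effects in 8a (8b) | Yes |
| 3-4 h | Maximum analgesic effect of Exparel (3) | Nothing described |
| Discharge to 72 h | Stated duration of Exparel (3, 6a); call at 48 h (4c) | Not among the four listed items |
| 7-14 days | Wound check, possibly with a local provider (4a) | No query and no return route stated |
| 10-14 days | Second call (4c) | Not among the four listed items |

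The side effects that the recovery hour is meant to screen for include constipation, which section 8a puts at roughly 10%. An hour in recovery cannot plausibly capture that, so the window does not fit the plan's own risk list either.

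**The plan's own figure.** No LAST rate or safety power is stated, so there is none to reproduce. The efficacy sample size (28% versus 50%, two-sided 0.05, 80% power, pooled variance, no continuity correction) reproduces at 76 per arm. Nothing below changes it.

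**What zero observed events would mean.** With n patients and every event detected, the one-sided 95% upper limit is 1 - 0.05^(1/n). If only a share d of events is detected, the limit on the true rate is that figure divided by d. The value of d is an assumption.

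| Exparel patients | d = 100% | d = 50% |
|---|---|---|
| 51 (half of the interim 102) | 5.7% | 11.4% |
| 76 | 3.9% | 7.7% |
| 100 | 3.0% | 5.9% |

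**Chance that the LAST rule sees at least one event (illustration only).** The formula is 1 - (1 - p·d)^n. Both the true rate p and d are assumptions, because the documents supply neither. The first figure counts 51 Exparel patients only. The second counts all 102, with the same p and d in both arms.

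| p | d = 100% | d = 50% | d = 25% |
|---|---|---|---|
| 0.1% | 5.0% / 9.7% | 2.5% / 5.0% | 1.3% / 2.5% |
| 0.5% | 23% / 40% | 12% / 23% | 6% / 12% |
| 1% | 40% / 64% | 23% / 40% | 12% / 23% |
| 2% | 64% / 87% | 40% / 64% | 23% / 40% |

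The halt applies to any episode in the trial. If p = 1% in both arms, all control events are seen and a quarter of Exparel events are seen, the chance is 1 - 0.99^51 × 0.9975^51 = 47%, against 64% with full detection.

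**All-cause check.** Suppose the rule is applied to all 102 interim patients with an exact two-sided 95% interval (the plan states neither). It is then first met at 17 complications: 17/102 = 16.7%, lower bound 10.02%. At 16 the bound is 9.24%. Near that point, one unreported complication changes the outcome of the check.

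**The case against.** The strongest case against is that the timing figures do not describe toxicity. The 3-4 hours is time to maximum analgesic effect, and the 72 hours is local retention and duration. The documents give no systemic exposure or onset of toxicity for either drug. A reader might infer that events are undercounted mainly in the Exparel arm, or that one hour is enough for plain bupivacaine. The text supports neither statement. This objection stands: a by-arm difference is plausible but not shown.

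The plan also calls LAST extremely uncommon in earlier trials. At 0.1% the halt would seldom be triggered even with perfect detection, as the table shows. That limits how many events could be missed. It does not help a rule that depends on catching one.

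A reader might also infer that toxicity is watched for only in recovery, or that the callers will not ask. Intraoperative monitoring is described too, one hour is a minimum, and spontaneous reports remain possible. The call script is not in the documents, Figure 1 is not shown, and the interim text says LAST symptoms were evaluated, so some collection was intended. The accurate statement is that toxicity is not listed among the call items and that no method of collection is given.

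Finally, the wound check is a natural occasion to find surgical complications, and nothing suggests that losses there differ by arm. What remains is that no step brings a local provider's findings back to the trial.

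**Conclusion.** The ascertainment gap is real. A primary safety endpoint that is also a halt trigger has no stated definition, no assessment window and no listed post-discharge question. Post-discharge LAST events and complications may be missed, plausibly more often with Exparel. Neither the direction nor the size can be established, because the documents give no LAST rate, onset timing or detection share. The probabilities above rest on assumed rates and detection shares and are not estimates.

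The consequence that can be stated is that a finding of no LAST, a finding of no difference, and both interim safety checks would rest on counts of unknown completeness. The powered outcome, the 48-hour opiate-free rate, is unaffected. This should be fixed, but it does not invalidate the design.

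**What to change.** - **Calls (4c).** In both arms and at both existing calls, ask the same short set of questions: toxicity symptoms that a family can report, with time of onset; any complication; any unplanned visit; any finding at a local wound check.
- **LAST endpoint (7a).** State the pre-defined LAST definition and an assessment window covering at least the 72 hours the protocol cites. The 48-hour call cannot cover all of that, so onset up to 72 hours would be completed by recall at the 10-14 day call.
- **All-cause complications (7c).** Count them up to the 10-14 day call, and state the patients and the interval method used for the 10% check.
- **Review before counting.** Compare reported symptoms with the LAST definition, without knowledge of arm where possible, before they enter the endpoint or the interim rule. Otherwise one unreviewed, non-specific symptom could halt the trial. Some items in 8a, such as AV block, cannot be reported by telephone and need a record of any visit.

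The cost is a few questions on calls already planned, some added endpoint wording, more non-specific symptom reports and some review work. Recall at 10-14 days is imperfect, but better than no question. Sample size and visits are unchanged, and no change to clinical observation is proposed.
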